## 6.9 Receipt of other Recommended Vaccines

At the final visit, Day 14, arrangements will be made to facilitate receipt of initial ACIP recommended vaccines for 2 month olds if they have not already received them prior to Visit 1. See tables below to reference the recommended ages and time intervals between vaccine doses:

Study Visit 1	Study Visit 3	Primary MD Visit (not part of study)
RV Immunization	"2 month" Immunizations	"4 month" Immunizations*
6 weeks	8 weeks	12 weeks
7 weeks	9 weeks	13 weeks
8 weeks	10 weeks	14 weeks
9 weeks	11 weeks	15 weeks
10 weeks	12 weeks	16 weeks
11 weeks	13 weeks	17 weeks
12 weeks	14 weeks	18 weeks

\*minimum of 4 week interval between immunizations

Recommended and minimum ages and intervals between vaccine doses				
Vaccine and dose number	Recommended age for this dose	Minimum age for this dose	Recommended interval to next dose	Minimum interval to next dose
HepB-1	Birth	Birth	1-4 months	4 weeks
HepB-2	1-2 months	4 weeks	2-17 months	8 weeks
DTaP-1	2 months	6 weeks	2 months	4 weeks
DTaP-2	4 months	10 weeks	2 months	4 weeks
Hib-1	2 months	6 weeks	2 months	4 weeks
Hib-2	4 months	10 weeks	2 months	4 weeks
IPV-1	2 months	6 weeks	2 months	4 weeks
IPV-2	4 months	10 weeks	2-14 months	4 weeks
PCV13-1	2 months	6 weeks	8 weeks	4 weeks

PCV13-2	4 months	10 weeks	8 weeks	4 weeks
---------	----------	----------	---------	---------

### Assurance of Rotavirus Vaccine Series Completion with Same Brand

The ACIP recommends that the rotavirus vaccine series be completed with the same product whenever possible (all RV1 or all RV5). We have established procedures to make every effort for children in the study to complete the rotavirus vaccine series with the same brand used for the first dose in the study. We will provide the parent and their infant's health care provider with written and electronic/fax documentation respectively of the dates, types, route, dose and manufacturer of vaccines given and will enter these into the CCHMC electronic medical record (immunization section and encounter note) as well as the Ohio State Registry IMPACT system. We will offer the parents to return to receive the same brand dose if they do not receive their care at CCHMC and their primary care provider does not offer the same brand. For children receiving their care at CCHMC, we will provide their primary care provider with the same brand dose. These additional doses of rotavirus vaccines will not be considered a study procedure.

**6.10 Study Compensation** Parents will be compensated for their time, effort and travel while in the study. The compensation provided will be based on the standard amounts decided on by CCHMC for research subjects who undergo the procedures outlined in this study and the time involved in the clinic visits and collection of samples and reactogenicity data at home. Payments will be given in the form of a debit card (ClinCard). We will load payment onto the ClinCard after each clinic visit that is completed.

- \$150 at 1st Clinic Visit
- \$150 at 2nd Clinic Visit
- \$100 at 3rd Clinic Visit
- \$50 if asked to come in for an unscheduled visit

If parent comes in for a clinic visit and the child is not eligible, they will receive \$25. If unable to complete the study, they will be paid for each study visit completed.

## STUDY VACCINE PRODUCT

### 7.1 Study Product Description, Storage and Stability

See the following links for study product package inserts. Since the focus of the study is rotavirus vaccine, we have provided details about dosage preparation and administration of RV1 and RV5. Other standard vaccines will be administered according to standard practice.

<https://www.gsksource.com/gskprm/htdocs/.../ROTARIX-PI-PIL.PDF>

[https://www.merck.com/product/usa/pi.../r/rotateq/rotateq\\_pi.pdf](https://www.merck.com/product/usa/pi.../r/rotateq/rotateq_pi.pdf)

### 7.2 Dosage, Preparation, and Administration of Study Product

#### RotaTeq®

Each 2-mL dose is supplied in a container consisting of a squeezable plastic, latex-free dosing tube with a twist-off cap, allowing for direct oral administration (RotaTeq® 2009).

To administer the vaccine:

1. Tear open the pouch and remove the dosing tube.
2. Clear the fluid from the dispensing tip by holding the tube vertically and tapping the cap.
3. Open the dosing tube in 2 easy motions:
  - a. Puncture the dispensing tip by screwing the cap *clockwise* until it becomes tight.
  - b. Remove the cap by turning it *counterclockwise*
4. Administer dose by gently squeezing the liquid into the infant's mouth toward the inner cheek until the dosing tube is empty. (A residual drop may remain in the tip of the tube.)

If for any reason an incomplete dose is administered (e.g., infant spits or regurgitates the vaccine), a replacement dose will not be administered. The infant should continue to receive any remaining doses in the recommended series. There are no restrictions on the infant's consumption of food or liquid, including breast milk, either before or after vaccination with RotaTeq® (RotaTeq® 2009).

### **Rotarix®**

Each 1-mL dose consists of a vial of lyophilized vaccine to be reconstituted with a liquid diluent in a prefilled oral applicator, allowing for direct oral administration (Rotarix® 2009).

To administer the vaccine:

1. Remove the vial cap and push the transfer adapter onto the vial (lyophilized vaccine).
2. Shake the diluent in the oral applicator (white, turbid suspension). Connect the oral applicator to the transfer adapter.
3. Push the plunger of the oral applicator to transfer the diluent into the vial. The suspension will appear white and turbid.
4. Withdraw the vaccine into oral applicator.
5. Twist and remove the oral applicator.
6. Administer Rotarix® orally.

In the event that the infant spits out or regurgitates most of the vaccine dose, a replacement dose will not be administered. There are no restrictions on the infant's food or liquid consumption, including breast milk, either before or after vaccination with Rotarix® (Rotarix® 2009).

## **7.3 Assessment of Subject Compliance With Study Product**

The study vaccines, RotaTeq® and Rotarix®, will be administered by the study product administrator, who is licensed to administer the vaccine (e.g., LPN [licensed practical nurse], RN [registered nurse], NP [nurse practitioner], PA [physician assistant], or medical doctor [MD]), in the clinic. Study personnel will record the administration time on the CRF and include whether it was a complete dose or a partial dose due to regurgitation.

## **8 LABORATORY EVALUATIONS AND METHODS**

### **8.1 Blood-Cytokine and Inflammatory Responses and Antibody Testing (IgG and IgA)**

Blood specimens from Visit 1 will be used for assessment of anti-rotavirus IgG antibody (maternal) and anti-rotavirus IgA antibody to rotavirus and measurement of serum cytokine levels and on the day of the second MRI (Visit 2) for measurement of serum cytokine levels and anti-rotavirus IgA. Blood for the antibody assays will be drawn into a serum separator tube by venipuncture (2-3 mL). After collection, the tubes will be kept at room temperature until the blood has clotted. The tubes will be centrifuged at room temperature at approximately 1000-1300g (2,400-2,700 RPM) for 10-15 minutes to ensure the sample is sufficiently separated. The serum will be removed using sterile glass or plastic pipets and aliquoted into

appropriately labeled cryovials (approximately 3 x 0.5 mL). The serum aliquots will be stored at -20 °C or colder until testing. The cytokines of interest will be assayed in a multiplex Luminex assay using the serum samples (Nefertiti C. DuPont et al 2005). The following cytokines will be measured: IL-2, IL-6, IL-7, IL-8, IL-15, INF- $\gamma$  and TNF- $\alpha$ . In addition, a C-reactive protein (pre- and post-vaccination) will also be done. Additional cytokines or biomarkers may be done should funding become available.

Maternal antibodies to rotavirus will be measured using an anti-rotavirus IgG ELISA assay developed and qualified in the Laboratory for Specialized Clinical Studies (LSCS). The antibody enzyme immunoassay will be used to detect and quantify rotavirus IgG antibody concentrations in human serum^112. Each assay will include a serially diluted 8-point standard curve generated by a reference standard consisting of a human serum pool arbitrarily assigned as having 1000 Units/mL. The curve will be modeled using the 4-parameter logistic fit regression function. Samples will be tested at 4 different concentrations. Dilution-corrected titers will be reported for the sample using the quantifiable range of the standard curve. Serum anti-rotavirus IgA will be determined using the same assay but using an anti-human IgA conjugate.

## 8.2 Stool-RV1 and RV5 Shedding and Cytokine Responses

Stool specimens will be utilized for both assessment of rotavirus vaccine shedding patterns and measurement of stool cytokines. For stool cytokine testing, stool specimens from Visit 1 and Visit 2 will be used. For assessment of rotavirus vaccine virus shedding patterns, all collected stools will be analyzed. Cytokine testing will be done on Visit 1 and Visit 2 specimens only. All stool samples will be kept frozen at -20 °C or colder until testing. For determination of rotavirus shedding and cytokine responses, stools will be thawed and nucleic acids will be extracted. For cytokine determination, PCR will be performed using Taqman gene expression assays from Life Technology for each of the cytokines of interest. The following cytokines will be done: IL-2, IL-6, IL-7, IL-8, IL-15, INF- $\gamma$  and TNF- $\alpha$ . Additional biomarkers or cytokines may be done should funding become available.

## 8.3 Saliva-DNA Genotyping for Secretor Status

Extracted DNA from the saliva will be tested to determine the child's secretor status by genotyping. Assay plates can accommodate up to 96 subjects each. We anticipate a yield of 25-30 ug of DNA per child using Oragene solution, which is more than sufficient for the purposes of this analysis. Secretor genotype will be determined at CCHMC through testing for known single nucleotide polymorphisms of the secretor gene (*FUT2*), 428G>A.

## 8.4 Breast Milk-IgA Antibody and Secretor Status of the Mother

Breast milk samples will be used to assess anti-rotavirus IgA antibody and secretor status of the mother. The anti-rotavirus IgA assay is a validated, standard ELISA assay that has been used for both RV1 and RV5 clinical trials by our lab (LSCS). We will also evaluate the mother's secretor status from breast milk using the genotyping method described above.

## 8.5 Future Testing

The informed consent form includes information about specimen storage and future use of the stored specimens. Samples will be retained for possible future testing with a linkage to identifiers. The samples will be stored locally at the site and local site investigators will have access to the samples. However, before the use of these samples by any investigator(s), request for use of these samples will require project approval by the CDC. The stool, saliva, serum, breast milk and DNA samples will be banked for future testing beyond the defined scope of this project; the consent forms will specifically include consent for banking samples for future use. Potential testing that could be done if funding were available includes (but is not limited to) testing of additional biomarkers or cytokines in the stool and blood as well as examining changes to the stool microbiome pre- and post-vaccination.

## 9 IMAGING METHODS

### 9.1 MR Imaging

#### 9.12 Methods

Anatomic imaging will be acquired with axial and coronal T2-weighted sequences. Motility will be evaluated using dynamic high spatial resolution 2D balanced steady state free precession (bSSFP) imaging. Coronal and axial balanced steady state images will be acquired during free breathing with an acquired temporal resolution of approximately 0.6s/image over 85 seconds. Diffusion weighted imaging will also be acquired using multiple b-values in order to evaluate any changes in diffusion restriction within the bowel wall or mesenteric lymph nodes between the two MRI exams.

#### 9.13 Image Interpretation

**Anatomic imaging** will be assessed by a pediatric radiologist with expertise in abdominal imaging ([name]). The well-distended distal/terminal ileum bowel wall thickness will be measured in 3 locations, and a mean wall thickness value will be obtained on each exam. The largest visible right lower quadrant mesenteric lymph nodes will be measured in short axis on each exam. Any secondary signs of inflammation (perienteric fat stranding, engorged vasa recta, free fluid) will be documented on each exam. After completion of the primary anatomic review by [name], a second pediatric radiologist with expertise in abdominal imaging will perform the same review on a random subset of subjects in order to determine inter-reader reliability. The second reviewer will be blinded to the initial assessment as well as to the time point of imaging.

**Motility imaging** will be assessed as follows: First, a quantitative assessment will be performed. A well-distended segment of distal/terminal ileum will be chosen by the first reviewer ([name]). Novel, semi-automated software, will be utilized to assess the coronal cine sequences in this investigation. No pre-market submission to the FDA has been made for the software nor are there any current plans to do so in the future. The semi-automated method computes a cross sectional area across time and the creates a best fit curve to determine the frequency or frequencies of contraction. After reviewer 1 identifies the bowel segment of interest, a post processing assistant will draw a region of interest on the bowel lumen on every image of the sequence. The application then creates a map of luminal cross-sectional area over time. The area versus time waveforms can be submitted to secondary analysis from which contraction frequency and other quantitative metrics of interest can be extracted.

Next a qualitative assessment will be performed. The research assistant will create a movie file for each subject, randomize the timepoints, and then insert the movie file into a PowerPoint presentation. The two reviewers, along with a third reviewer (a pediatric gastroenterologist with expertise in gut motility) will review the images to determine which movie has faster motility, and for each movie, if the motility is organized or disorganized. Finally, each of the three reviewers will assess the focal segment of the distal/terminal ileum in the same manner.

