## **2.2 Intestinal Imaging**

### **Imaging Studies in Children with Rotavirus Infection**

Two previous studies have been done in children to explore possible mechanisms for the cause of intussusception in children with wild-type rotavirus infection. In the first study, 13 children with confirmed rotavirus infection were age- and sex-matched to healthy children and ultrasound measurements were done to assess ileum wall thickness and mesenteric lymph node diameters at enrollment and one month later; motility was not assessed. The average age at enrollment was comparable (7.2 months for cases and 7.3 months for controls). They found children with rotavirus infection to have significantly thicker ileum wall thickness, greater lymph node size and number of nodal aggregates and greater free fluid compared to controls. While distal ileum loops were visualized in all study subjects, the terminal ileum was only visualized in 46% of patients with rotavirus infection and in 62% of controls. They concluded that these changes suggested a mechanism by which rotavirus could cause intussusception. Since most intussusception occurs at the terminal ileum, it is critical that an

imaging study evaluating risk for intussusception can effectively image this area. With MRI, we will be able to visualize and measure the wall of the terminal ileum for all patients as well as assess motility.

In a second study, investigators enrolled five children with symptomatic rotavirus infection and did imaging with ultrasound and MRI within 5 days of the onset of symptoms and repeated imaging 5-9 weeks later with an age range of 8-20 months (mean age of 14 months). They found three of the five infants had a significantly thicker ileal wall thickness in the acute period compared to the convalescent period but no differences in the number and size of mesenteric lymph nodes. They found no difference in peristaltic activity between the two time periods using MRI imaging without sedation. The authors did not appear to have a period where the infants were made NPO. A small sample size (4 infants for the MRI) and lack of a specific protocol for feeding may have impacted their ability to assess motility patterns.

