#### 9.22 Image Interpretation

**Anatomic imaging** will be assessed by a pediatric radiologist with expertise in abdominal imaging ([name]). The well-distended distal/terminal ileum bowel and cecum wall thickness will be measured in 3

locations, and a mean wall thickness value will be obtained on each exam. The largest right lower quadrant mesenteric lymph nodes will be measured in short axis on each exam. Any secondary signs of inflammation (perienteric fat stranding, engorged vasa recta, free fluid) will be documented on each exam.

After completion of the primary anatomic review, a second pediatric radiologist with expertise in abdominal imaging will perform the same review on a random subset of subjects in order to determine inter-reader reliability. The second reviewer will be blinded to the initial assessment as well as to the time point of imaging.

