**b) Inferential statistics**

The primary analysis for this study is the comparison of anatomical outcome as measured by MRI between (RV1, RV5 with and without other vaccines: 4 groups) and within (pre and post) study groups. The primary anatomical outcome will be the terminal ileum thickness measured in mm. The change in this outcome before and after vaccination will be compared for each study group (within group test) using a paired t-test, while the between group difference at pre, post and on the difference between pre and post (change score) will be initially analyzed using general linear model (GLM) where the ileum thickness (at pre, post and change score) is modeled as a function of group (4-groups). Depending on the result of the F-test from the GLM analysis, this will be followed by pairwise comparison between groups (6-comparisons). This will be examined using a two sample t-test. If the difference between groups with and without other vaccines for a given vaccine (RV1 or RV5) is not significant we might combine the categories and conduct a comparison test for the outcome between the two vaccine types. If the primary outcome is not normal before or after transformation we will use the non-parametric Kruskal-Wallis test to compare the groups. Although the primary between group comparisons is based on the pre-post change score, we are conducting additional analysis based on the pre and post data to get more insight about the distribution of the primary outcome variable.

We will also examine the distribution of socio-demographic and other potential covariates among the groups using a GLM analysis. If some covariates are differentially distributed among the groups, those covariates will be controlled for in the primary analysis described above. Potential modifiers such as breast milk or secretor status will be examined by modeling the primary outcome as a function of group, potential modifier and the interaction between group and modifier. In this case the parameter of interest is the coefficient of the interaction term, however it is possible that the interaction test might not be sensitive due to sample size. Regardless we will examine and report the observed change between groups for each potential modifier as a subgroup. For example we will report difference between groups in the primary outcome for secretors and non-secretors separately.

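### The primary outcome is the change in terminal ileum thickness, but the MRI reading rule neither fixes the terminal ileum as the site nor requires the same segment on both exams

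*Combined protocol and SAP*

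**What the plan says.** Section 10.3, Inferential statistics, defines the endpoint: "The primary anatomical outcome will be the terminal ileum thickness measured in mm". It is analysed as a change, both within groups ("The change in this outcome before and after vaccination will be compared for each study group (within group test) using a paired t-test") and between them ("Although the primary between group comparisons is based on the pre-post change score").

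Section 9.13 is where the protocol says how wall thickness is read on MRI: "The well-distended distal/terminal ileum bowel wall thickness will be measured in 3 locations, and a mean wall thickness value". The reading is per exam: "a mean wall thickness value will be obtained on each exam". The three locations are not tied to a landmark. A second radiologist "will perform the same review on a random subset of subjects in order to determine inter-reader reliability", and that reader is blind to the first assessment and to the time point. No such statement is made for the primary reader. Section 10.1 blinds the study radiologists to arm, not to visit.

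Section 2.2, describing an earlier ultrasound study, separates the two sites: "While distal ileum loops were visualized in all study subjects, the terminal ileum was only visualized in 46% of patients with rotavirus infection". Among its controls the figure was 62%. The same section calls imaging of the terminal ileum critical, because most intussusception occurs there, and expects MRI to allow its wall to be measured in all patients.

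For ultrasound, Section 9.21 names the terminal ileum as the target, while Section 9.22 widens the site as 9.13 does: "The well-distended distal/terminal ileum bowel and cecum wall thickness will be measured in 3" locations.

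**The concern.** The endpoint names one site and the reading rule accepts two. A reader who follows Section 9.13 to the letter may measure terminal ileum at Visit 1 and a more proximal distal loop at Visit 2, or the reverse, because the stated condition is that the bowel be well distended. The change score would then include a difference between sites that has nothing to do with vaccination. Where a distal loop is read at both visits, the pair is consistent but would still be reported as a terminal ileum result.

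This matters most for the within-group tests. All four arms receive a rotavirus vaccine (Section 4.1), so any statement about the effect of RV1 or RV5 itself rests on an uncontrolled comparison of before with after. A shift in segment choice with visit would look like a vaccine effect. The trial's own hypothesis (Section 3.2) is that vaccine may alter motility. Altered motility could plausibly change which segment is well distended on Day 5. The Power section also says that effect sizes will be reported to help design later studies, so a mixed-segment mean or SD would be carried forward.

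**Working it through.** The plan states no SD, effect size or power for this outcome, and the Power section says that no calculation was made. There is therefore no figure to reproduce. The check is textual, followed by algebra showing which comparisons are exposed.

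**Text, side by side**

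- Site in the endpoint (10.3): terminal ileum.
- Site in the MRI reading rule (9.13): well-distended distal or terminal ileum.
- Are these one site? Section 2.2 reports visibility of 100% for distal loops against 46% and 62% for terminal ileum in the same children, so the protocol itself treats them as different.
- Unit of reading (9.13): one mean per exam. No matching across exams, no record of the segment read, and no instruction for a terminal ileum that is poorly distended on one exam.
- Places that might close the gap: Section 6.6 standardises preparation but names no segment. Section 9.12 covers sequences. Section 9.21 concerns ultrasound only. Section 10.1 concerns arm. The second reader covers a subset and tests agreement between readers. None requires the same segment at both visits.
- Averaging three locations reduces noise within a segment. It does not remove a difference between segments.

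**Algebra**

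Let the SD of a matched-segment change be 1, m the share of infants whose two exams are read on different segments, and D the thickness difference between the segments in those SD units.

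- Mismatch in either direction equally: no bias, and the variance of the change becomes 1 + m·D².
- Mismatch all in one direction: the within-group mean change is biased by m·D.
- Between arms A and B under one-way mismatch: the bias is (m_A − m_B)·D, which is zero when the shares are equal.

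Noise thus affects every comparison. Bias affects the within-group tests if mismatch follows visit, and the randomised comparisons only if it differs by arm.

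**Can a size be given?**

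Neither m nor D is in the documents. Purely as assumptions, take m from 0.10 to 0.50 and D from 0.5 to 1.5:

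- SD multiplier: √(1 + 0.10 × 0.25) = 1.01, up to √(1 + 0.50 × 2.25) = 1.46.
- Within-group bias if all one way: 0.10 × 0.5 = 0.05 SD, up to 0.50 × 1.5 = 0.75 SD.
- With 37 per group (150 / 4 = 37.5) and an assumed two-sided 5% test, the between-group difference that has 80% power with matched segments is (1.96 + 0.84) × √(2/37) = 0.65 SD. Its power becomes 79% at the mild end and 49% at the severe end.

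The range runs from negligible to serious, so the arithmetic shows the mechanism and gives no estimate of size. Even 37 per group is a ceiling: the 70% benchmark for completing both MRIs (Appendix 2) corresponds to 0.70 × 37.5 ≈ 26 pairs per group.

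**The case against.** The best defence is that mismatch may be rare. Section 2.2 expects the terminal ileum to be measurable on MRI in all patients. One radiologist does the primary review and may well match segments without being told to. Section 6.6 sets a weight-based contrast volume, a fixed feeding time and the same fasting instruction for both visits, which limits day-to-day variation in distension. The motility route to bias is only a hypothesis: Section 2.2 cites a small study of infected children with no difference in peristaltic activity, and the mouse work cited in the background found no effect of infection on transit. All of this stands as a reason to expect a modest problem. None of it is a reading rule, and if the expectation holds, the fix costs almost nothing.

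Several stronger readings are tempting, and the documents do not support them.

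- A reader might infer that any bowel loop may be measured. The rule is confined to well-distended distal or terminal ileum, and the slash can be read as one region at the end of the ileum.
- A reader might take 46% and 62% as the expected MRI success rates. They come from an outside ultrasound study of infants averaging about 7 months, some with rotavirus infection. Here they show only that the two sites are distinct.
- A reader might infer that ultrasound pools ileum and cecum into one mean. That is a strained reading of Section 9.22, since Section 10.3 lists cecum thickness as its own parameter.

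**Conclusion.** The text establishes that the endpoint and the reading rule do not name the same site, and that nothing ties the two exams to one segment or hides the time point from the primary reader. A primary change score can therefore compare different segments, or report a distal loop as terminal ileum.

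The consequence is added noise in the between-group comparisons and possible bias in the uncontrolled within-group paired tests if segment choice shifts with visit. A reader might infer that the randomised comparisons are biased too. That would need mismatch to differ by arm, which nothing in the documents shows. A reader might also want to state a loss of effective sample size or a bias in SDs. The documents supply neither the frequency of mismatch nor the difference between sites, so no such figure is justified. The expectation about MRI in Section 2.2 suggests that mismatch may be infrequent.

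The point is worth fixing because it concerns the primary outcome and the remedy is cheap. It does not show that the results would be unreliable.

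**What to change.** In Section 9.13:

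- Name the terminal ileum as the target site.
- Have the primary reader measure the same segment on both exams, with the two exams presented in random coded order and the time point hidden. Section 9.13 already has time points randomised for the motility movies.
- Record on the read form which segment (terminal or other distal ileum) was measured at each of the three locations.

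In Section 10.3:

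- Keep all infants with both MRIs in the primary analysis.
- Add a sensitivity analysis limited to pairs with terminal ileum read on both exams, and report the number of unmatched pairs by arm.

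The primary analysis should not itself be restricted to terminal ileum pairs. That would exclude infants after randomisation on an imaging feature that vaccination might affect. For the same reason, the restricted result should be read only as a sensitivity analysis.

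For the MRI-ultrasound comparison, compare the same named segment in both modalities.

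The cost is one extra field on the read form and slightly more reading and analysis work, with no extra scans. The recorded segment also yields a feasibility figure that Appendix 2 lacks: the share of infants with a measurable terminal ileum on both MRIs.
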